7.3 Safety Evaluation

Acute or late toxicity will be assessed and scored using CTCAE version 5.0 and recorded in the eCRF. More specifically, subjects will be questioned at each follow-up visit regarding AE and they will be instructed to inform the investigator or study personnel of any AE occurring at any time during the trial.

Moreover, the patient's Karnofsky performance score will be evaluated during every follow-up visit.

7.4 Patient reported outcome

The patient will report on his quality of life (QoL) by completing the EORTC QLQ-C15-PAL and the EuroQol Group EQ-5D-5L questionnaires in Dutch, English or French depending on the native language of the patient (see appendix 2 and appendix 3). These questionnaires will preferentially be completed digitally, but will also be available on paper.

All patient reported outcome (PRO) assessments should be completed before any other tests, procedures, or other consultations, to prevent influencing participant perceptions. Relevant actual dates and times of assessments will be recorded in the source documentation and eCRF.

8. Safety management and reporting

The Investigator and any designees are responsible for detecting, documenting, and recording events that meet the definition of an AE or SAE and remain responsible for following up AE that are serious, considered related to the study treatment or study procedures, or that caused the subject to discontinue the study.

8.1 Definitions and criteria

8.1.1 Definition of an adverse event (AE)

An AE is any untoward medical occurrence in a subject, temporally associated with the use of study treatment, whether or not considered related to the study treatment. An AE can therefore be any unfavourable and unintended sign (including an abnormal laboratory finding), symptom, or disease (new or exacerbated) temporally associated with the use of study treatment.

8.1.2 Definition of a serious adverse event (SAE)

An SAE is defined as any untoward medical occurrence that, at any dose:

HERMES/CTO23032GZA – Protocol v3.0 07-OCT-2024

44/70

Clinical Trials Oncology

Ref.Nr.: P.01-S.23

Versie: 6.0

- results in death
- is life-threatening
The term 'life-threatening' in the definition of "serious" refers to an event in which the subject was at risk of death at the time of the event. It does not refer to an event, which hypothetically might have caused death, if it were more severe.
- requires in-patient hospitalization or prolongation of existing hospitalization
In general, hospitalisation signifies that the patient has been detained (usually involving at least an overnight stay) at the hospital or emergency ward for observation and/or treatment that would not have been appropriate in the physician's office or outpatient setting. Complications that occur during hospitalisation are AE. If a complication prolongs hospitalisation or fulfils any other serious criteria, the event is serious. When in doubt as to whether "hospitalisation" occurred or was necessary, the AE should be considered serious. Hospitalisation for elective treatment of a pre-existing condition that did not worsen from baseline is not considered an AE.
- results in persistent or significant disability/incapability
The term disability means a substantial disruption of a person's ability to conduct normal life functions.
This definition is not intended to include experiences of relatively minor medical significance such as uncomplicated headache, nausea, vomiting, diarrhea, influenza, and accidental trauma (e.g., sprained ankle) which may interfere with or prevent everyday life functions but do not constitute a substantial disruption.
- is a congenital anomaly or birth defect
- is medically important
Medical or scientific judgement should be exercised in deciding whether SAE reporting is appropriate in other situations such as important medical events that may not be immediately life-threatening or result in death or hospitalization but may jeopardize the patient or may require medical or surgical intervention to prevent 1 of the other outcomes listed in the above definition. These events should usually be considered serious.
Examples of such medical events include invasive or malignant cancers, intensive treatment in an emergency room or at home for allergic bronchospasm, blood dyscrasias or convulsions that do not result in hospitalization, or development of drug dependency or drug abuse.

8.1.3 Severity or intensity criteria

AE are to be recorded on the eCRF. Severity will be graded according to the CTCAE v 5.0, published November 27, 2017 (CTCAE v5.0 – see Appendix 4).

The Investigator will make an assessment of intensity for each AE and SAE reported during the study and assign it to 1 of the following categories:

- **Grade 1:** Mild; an event that is easily tolerated by the subject, causing minimal discomfort and not interfering with everyday activities.
- **Grade 2:** Moderate; an event that causes sufficient discomfort and interferes with normal everyday activities.

- **Grade 3:** Severe; an event that prevents normal everyday activities.
- **Note:** An AE that is assessed as severe should not be confused with a SAE. Severe is a category utilised for rating the intensity of an event; and both AE and SAE can be assessed as severe.
- **Grade 4:** Life-threatening consequences; urgent intervention indicated
- **Grade 5:** Death related to AE.

An event is defined as ‘serious’ when it meets at least 1 of the predefined outcomes as described in the definition of an SAE, NOT when it is rated as severe.

8.1.4 Causal relationship of an AE/SAE to the intervention

The Investigator is obligated, and will use clinical judgement, to assess the relationship between study treatment and each occurrence of each AE/SAE. Furthermore, the investigator will assess the relationship between the bone metastatic disease and each occurrence of each AE/SAE. Only AE/SAE that are related to the bone metastatic disease or related to radiotherapy (only applicable for patients in arm B) will be reported using the National Cancer Institute Common Terminology Criteria for Adverse Events (NCI-CTCAE) v5.0 (see appendix 4). The relationship of each AE/SAE to the study intervention should be characterized using one of the following: related to RT, related to bone metastatic disease or unrelated.

Table 3 Adverse event causal relationship with study treatment

Related to RT (only applicable for patients in arm B)	There is a reasonable possibility that the RT is the cause of the AE.
Related to bone metastatic disease	There is a reasonable possibility that the bone metastatic disease is the cause of the AE.
Unrelated	There is no reasonable possibility that the RT or the bone metastatic disease is the cause of the AE.

8.1.5 Expectedness of an SAE:

The following definitions are general guidelines to help assign grade of attribution:

Adverse reaction (AR): any AE caused by a study treatment.

Suspected adverse reaction (SAR): any AE for which there is a reasonable possibility that the study treatment caused the AE.

Unexpected: an event is considered unexpected if its nature or severity is not consistent with a recognized side-effect of the study treatment.

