8.2.2 Period for collecting AE and SAE information

During the period from main ICF signing to the last follow-up visit (24m after randomization date), date of death of any cause or early end of participation in the study due to other reasons, all (S)AE that are related to the bone metastatic disease or related to radiotherapy (only applicable for patients in arm B) will be documented in both study arms.

The following applies for (S)AE related to RT (arm B):

Toxicity that appears within 90 days after the last RT dose will be regarded as acute toxicity.

Toxicity that appears >90 days after the last RT dose administration will be regarded as late toxicity.

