9.3 Statistical methods for analysing primary and secondary outcomes

Primary objective:

The primary endpoint (SSE-free survival) is a composite endpoint of SSEs and death (death before SSE is part of the endpoint, not a competing risk). The primary endpoint is time until the occurrence of SSE in any bone metastasis or death from the date of randomization whichever occurs first. Data suggest that the median SSE-free survival is around 10.4 months. With a HR of 0.5, we hypothesize that the median SSE-free survival will be 20.8 months.

A proportion of patients will have multiple high-risk bone lesions. Pain will be reported lesion-based, however the SSE-free survival remains patient-based as this is more clinically relevant.

Secondary objectives

- The number of **hospitalizations** related to the high-risk metastase(s) will be compared between systemic therapy / observation (arm A) and upfront RT plus systemic therapy / observation (arm B) from date of study randomization to last follow-up visit (24m after randomization date), date of death of any cause or early end of participation in the study due to other reasons
- **Overall survival** will be assessed from time of study randomization to date of death of any cause or last follow-up visit (24m after randomization date)
- **Quality of life** will be compared between systemic therapy / observation (arm A) and upfront RT plus systemic therapy / observation (arm B), using the EORTC QLQ-C15-PAL questionnaire (see appendix 2) and the EuroQol Group EQ-5D-5L questionnaire (see appendix 3)
- **Adverse events** in both study arms will be evaluated using the National Cancer Institute Common Terminology Criteria for Adverse Events (NCI-CTCAE) v5.0 (see appendix 4) from the time of ICF signing to last follow-up visit (24m after randomization date), date of death of any cause or early end of participation in the study due to other reasons. Only adverse events that are related to the bone metastatic disease or related to the radiotherapy (only for patients in arm B) will be reported in the eCRF.

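### Section 8.1.4 asks for two causality assessments per adverse event but keeps one code, so arm B events with two plausible causes may be lost from the RT-attributed toxicity count

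*Protocol*

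**What the plan says.** Protocol section 8.1.4 first obliges the investigator to assess the relationship of each event to study treatment. It then adds a second assessment: "Furthermore, the investigator will assess the relationship between the bone metastatic disease and each occurrence of each AE/SAE". The recording rule that follows allows one answer only. The relationship "should be characterized using one of the following: related to RT, related to bone metastatic disease or unrelated".

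The table in 8.1.4 (headed Table 3 there, a number also used for the NRF model in 5.1) defines the codes:

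- The RT code, for arm B only, applies when "There is a reasonable possibility that the RT is the cause of the AE".
- The bone-disease code, open to both arms, sets the same threshold: "There is a reasonable possibility that the bone metastatic disease is the cause of the AE".
- The third code, for unrelated events, applies when neither cause is a reasonable possibility.

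Three other places depend on this attribution or sit beside it:

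- Section 8.1.5 defines a suspected adverse reaction as "any AE for which there is a reasonable possibility that the study treatment caused the AE".
- Section 8.2.2 introduces the acute/late split with "The following applies for (S)AE related to RT (arm B") and then states: "Toxicity that appears >90 days after the last RT dose administration will be regarded as late toxicity".
- Section 9.3 sets the wider endpoint: "Adverse events in both study arms will be evaluated using the National Cancer Institute Common Terminology Criteria for Adverse Events". Events related to bone disease and events related to RT are both entered in the eCRF.

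**The concern.** The two related codes are not mutually exclusive, because each needs only a reasonable possibility of cause. An event at an irradiated metastasis can satisfy both. The recording rule then makes the investigator give up one of the two judgements that the same section has just required, without saying which.

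Acute and late toxicity is a stated secondary objective (section 2), and the acute/late label exists only for events related to RT. If a dual-cause event is coded to bone disease, it carries no such label and does not appear as RT toxicity. The code may also lead whoever screens for suspected reactions to pass over an event that meets the 8.1.5 definition. Treatment is open-label (5.2), so the choice is made by someone who knows the arm.

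This is a rule for collecting data. An analysis plan can decide how to tabulate the codes, but it cannot supply an attribution that was not recorded.

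**Working it through.** The plan states no figure on this point, so the check is mainly a comparison of texts.

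1. **Assessments required.** Section 8.1.4 requires two per event: to study treatment and to bone disease.
2. **Possible results in arm B.** Two yes/no judgements give four combinations:

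| RT a reasonable possibility | Bone disease a reasonable possibility | Code available in 8.1.4 |
|---|---|---|
| yes | no | related to RT |
| no | yes | related to bone metastatic disease |
| no | no | unrelated |
| yes | yes | none of its own; either related code fits |

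Four outcomes are mapped to three codes, and nothing says where the fourth goes.

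3. **Can the fourth row occur here?** Symptomatic pathological fracture and spinal cord compression are SSEs (sections 2 and 7.2), so the protocol expects bone disease to cause them. Section 5.1 names impending fracture as an example of when SABR may not be safe, which hints at RT risk in the same bone. That support is indirect: the protocol contains no list of RT side effects.
4. **Direction.** By the table's own definition, the first and fourth rows are RT-related. With that definition correctly applied, a forced single code leaves the first row unchanged and can only take events out of the fourth. The RT-attributed count can fall but cannot rise.
5. **What follows from a bone-disease code.** The event remains reportable and remains in the both-arm evaluation (8.2.2, 9.3). It gets no acute/late class, because 8.2.2 applies that to RT-related events only. It still meets 8.1.5, but the recorded code says something else.

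**Illustration only.** Take 60 patients in arm B (section 9.1) and at most one relevant event each. Let a be the proportion with an RT-only event, d the proportion with a dual-cause event, and q the share of dual-cause events coded to bone disease. The documents give none of a, d or q; all three are assumptions.

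RT-attributed patients = 60 × (a + d(1 − q)); loss = 60 × d × q.

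With a = 5%:

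| d | q = 0 | q = 0.5 | q = 1 |
|---|---|---|---|
| 5% | 6 | 4.5 | 3 |
| 10% | 9 | 6 | 3 |
| 15% | 12 | 7.5 | 3 |

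For example, d = 10% and q = 0.5 gives 60 × (0.05 + 0.10 × 0.5) = 6, against 60 × (0.05 + 0.10) = 9 with nothing lost. The loss does not depend on a. Over these values it runs from 0 (q = 0) to 60 × 0.15 × 1 = 9 patients. The range shows how sensitive the count is to q; it is not an estimate for this trial.

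**The case against.** The strongest reply is that nothing tells investigators to prefer bone disease. The RT code needs only a reasonable possibility, so a dual-cause event qualifies for it, and if every such event is coded to RT the RT count loses nothing. That is correct, and it is why the point is a risk of loss and not a certain one.

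Several stronger readings are tempting, and the documents do not support them.

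- *A reader might infer that dual-cause events leave the safety data.* They do not. Only unrelated events go unreported, and a dual-cause event cannot be unrelated under the table. Events coded to bone disease keep their CTCAE grade and count in the evaluation of both arms. A between-arm comparison that pools the two related codes is unaffected.
- *A reader might infer that such events are excluded from SUSAR reporting.* Section 8.1.5 has its own test and does not refer to the code. All SAEs go to the sponsor within 24 hours (8.2.3), and the sponsor is responsible for SUSAR reporting (8.2.4). The 7-day and 15-day limits cover unexpected reactions only; suspected serious reactions in general go into the annual report. What stands is that the recorded code can mislead that assessment, for either route.
- *A reader might infer that the loss is irrecoverable.* RT dates are captured (5.3), as is the location of SSE fractures and compressions (6.2), so a sensitivity analysis counting all recorded arm B events is possible. The missing item is the investigator's own second judgement.
- *A reader might infer that bone metastases and RT are known to produce the same events.* The protocol does not say so. Section 10.1.4 expects no or mild acute toxicity in most patients after conventional RT, and no high-grade side effects.

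**Conclusion.** The inconsistency in 8.1.4 is real: two assessments required, one recorded, overlapping definitions and no tie rule. The exposed quantities are the RT-attributed toxicity count with its acute/late split, which serves a secondary objective, and the identification of suspected adverse reactions. Against the table's own definition, any error in the RT-attributed count goes one way and makes RT look less toxic.

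The size cannot be derived, because the protocol gives neither the frequency of dual-cause events nor how investigators would code them. Any percentage of undercounting would only restate an assumed miscoding share. The conclusion assumes that the eCRF, which is not among the documents, follows the single-choice rule as written. The primary endpoint, the sample size and the capture of SSEs are not affected. The change should be made, since it is cheap and the attribution is best collected prospectively.

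**What to change.** In section 8.1.4 and in the eCRF, replace the single choice by two independent yes/no items for each (S)AE:

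- reasonable possibility caused by RT (arm B only);
- reasonable possibility caused by bone metastatic disease.

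Define unrelated as no to both. State that any yes for RT enters the acute/late classification in 8.2.2 and the SAR/SUSAR assessment under 8.1.5 and 8.2.4, whatever the answer to the second item.

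Two items are better than a precedence rule. Sending every dual-cause event to RT would protect the RT count, but would take those events out of arm B's bone-disease count, while arm A has no RT code to which such events could move.

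No added sentence on SSE status is needed. SSEs are defined and recorded without reference to the causality code (sections 2, 7.2 and 8.2.1).

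The cost is one extra eCRF field, a short rewording of 8.1.4 and its table, and possibly a slightly higher reported RT-related toxicity rate.

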8.1.6 Outcome

Outcome of an AE or SAE will be recorded on the AE eCRF as follows:

- Recovered/resolved
- Recovering/resolving

- Recovered/resolved with sequelae
- Not recovered/not resolving
- Fatal
- Unknown

8.2 Reporting procedures

8.2.1 Method of detecting (S)AE

AE will be reported by the subject. Care will be taken not to introduce bias when detecting AE and/or SAE. Open-ended and non-leading verbal questioning of the subject is the preferred method to inquire about AE occurrences. For each SAE, it should be evaluated whether it concerns an SSE. If it concerns an SSE, the SAE should be documented as such in the eCRF and the necessary actions should be taken (see section 6.2). In case hospitalization occurs, it should be evaluated whether the hospitalization is related to the high-risk bone metastasis(es) and this information should be documented in the eCRF.

8.2.2 Period for collecting AE and SAE information

During the period from main ICF signing to the last follow-up visit (24m after randomization date), date of death of any cause or early end of participation in the study due to other reasons, all (S)AE that are related to the bone metastatic disease or related to radiotherapy (only applicable for patients in arm B) will be documented in both study arms.

The following applies for (S)AE related to RT (arm B):

Toxicity that appears within 90 days after the last RT dose will be regarded as acute toxicity.

Toxicity that appears >90 days after the last RT dose administration will be regarded as late toxicity.

8.2.3 Investigator reporting of an (S)AE to the sponsor

When an AE/ SAE occurs, it is the responsibility of the Investigator to review all documentation (e.g., hospital progress notes, laboratory reports, and diagnostics reports) related to the event.

The Investigator will then record all relevant AE/ SAE information in the eCRF. Each event must be recorded separately.

There may be instances when copies of medical records for certain cases are requested by. In this case, all subject identifiers, with the exception of the subject number, will be redacted on the copies of the medical records before submission.

The Investigator will attempt to establish a diagnosis of the event based on signs, symptoms, and/or other clinical information. Whenever possible, the diagnosis (not the individual signs/symptoms) will be documented as the AE/ SAE.

The investigator shall report all serious adverse events immediately (<24h), after first knowledge, to the sponsor. Information regarding SAE will be transmitted to the sponsor using the SAE form, which must be completed and signed by a physician from the study site and transmitted to the sponsor ([contact]) within 24 hours. The investigator will submit any updated SAE data to the Sponsor within 24 hours of it being available.

All SAE that have not resolved by the end of the study or that have not resolved upon discontinuation of the subject's participation in the study, must be followed until any of the following occurs:

- the event resolves
- the event stabilizes
- the event returns to baseline, if a baseline value/status is available
- the event can be attributed to agents other than the treatment or to factors unrelated to study conduct
- it becomes unlikely that any additional information can be obtained (subject or health care practitioner refusal to provide additional information, lost to follow-up after demonstration of due diligence with follow-up efforts)

The immediate and follow-up SAE reports shall identify subjects by patient specific study numbers.

The following situations do not need to be reported as SAE:

- Elective hospitalization for pre-existing conditions that have not been exacerbated by the treatment;
- A hospitalization which was planned before the patient consented for study participation and where admission did not take longer than anticipated;
- Social and/or convenience admission to a hospital;
- Medical or surgical procedure, e.g., endoscopy, appendectomy; unless the condition that leads to the procedure is an (S)AE.
- Situations where an untoward medical occurrence did not occur (palliative care, rehabilitation, overdose without occurrence of an AE);
- Anticipated day-to-day fluctuations of pre-existing disease(s) or condition(s) present or detected at the start of the study that do not worsen.

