10.1.4 Benefit-risk assessment

This study will be performed in accordance with ethical principles that have their origin in the Declaration of Helsinki and are consistent with ICH, GCP, and applicable regulatory guidelines.

To further minimize any potential risk, careful monitoring of each subject will be conducted throughout the study to detect any adverse events (AE) or safety signals, as delineated in the schedule of events.

Potential risks of study participation

The intervention in this study is early, upfront radiation therapy to asymptomatic or minimally symptomatic bone metastases.

In general, a single fraction of 8 Gy will be prescribed according to general recommendations for patients with painful bone metastases. This single day treatment is characterized by its **limited patient burden**. Radiation dose and planning will follow international guidelines and will be delivered with contemporary radiation techniques, thereby **minimizing the side effects for** patients [Oldenburger et al, Nguyen et al, Lutz et al].

Potential benefits of study participation

The aim of this trial is reducing the number of SSEs, inherently a **symptom-based endpoint**. Therefore, the hypothesis of the project is to decrease symptoms and side effects for each individual patient.

Risk-benefit assessment

According to the ESTRO-ACROP recommendations, the majority of patients experience no or mild acute toxicity after conventional radiotherapy, the possibility of experiencing side effects should not be a reason to withhold patients with bone metastases from this treatment. No high-grade side effects are expected.

Patients in the observational arm will not receive RT but have the possibility to receive palliative RT to progressed, painful lesions (an SSE) only at the time of symptom worsening.

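### Section 8.2.3 exempts from SAE reporting an elective admission for a bone metastasis that has progressed naturally, which sections 8.1.2 and 8.2.2 treat as reportable

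*Protocol*

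**What the plan says.** Section 8.1.2 makes an event serious if, among other criteria, it "requires in-patient hospitalization or prolongation of existing hospitalization". It then carves out one kind of admission: "Hospitalisation for elective treatment of a pre-existing condition that did not worsen from baseline is not considered an AE". The test is whether the condition has worsened. What made it worse does not matter.

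Section 8.2.3 ends with a list of situations exempt from SAE reporting. One bullet reads "Elective hospitalization for pre-existing conditions that have not been exacerbated by the treatment". Here the test is cause: without exacerbation by the treatment, the admission is exempt.

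Three other places bear on the point:

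- Section 8.2.2 requires that "all (S)AE that are related to the bone metastatic disease or related to radiotherapy (only applicable for patients in arm B) will be documented", and says that this applies in both arms.
- The procedures bullet in the 8.2.3 list gives an exemption "unless the condition that leads to the procedure is an (S)AE".
- The last bullet of that list covers "Anticipated day-to-day fluctuations of pre-existing disease(s) or condition(s) present or detected at the start of the study that do not worsen".

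Section 8.2.3 does not define the treatment. Section 10.1.4 states: "The intervention in this study is early, upfront radiation therapy to asymptomatic or minimally symptomatic bone metastases". The causality table in section 8.1.4 has one row that begins "Related to RT (only applicable for patients in arm B" and a separate row for events caused by bone metastatic disease.

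**The concern.** Every patient enters with bone metastases, so a lesion that was present at baseline and has since progressed is an ordinary course in this population. Some of these patients may be admitted on a planned basis. For them the two exemptions give opposite answers, and a site can follow either section and believe that it complies.

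Two things are at stake. First, section 8.2.3 requires SAEs to reach the sponsor within 24 hours, and an admission that a site treats as exempt does not trigger that notice. Second, the trial is open-label (section 5.2) and adverse events in both arms are a secondary endpoint. A reporting threshold that turns on whether the treatment caused the worsening need not be the same in an arm that receives study RT and an arm that does not.

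**Working it through.** The protocol gives no figure for such admissions, so the check is a comparison of texts, followed by simple algebra on what each rule would count.

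**Step 1. Elective admission for a metastasis present at baseline, with the treatment read as study RT**

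| State of the lesion | 8.1.2 | 8.2.3 bullet | Possible in |
|---|---|---|---|
| Not worse than baseline | exempt | exempt | both arms |
| Worse, attributed to study RT | not exempt | not exempt | arm B only |
| Worse by natural progression | not exempt | exempt | both arms |

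The rules agree in the first two rows and contradict each other in the third.

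**Step 2. Which rule the rest of the protocol supports**

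Section 8.2.2 wants all (S)AE related to bone metastatic disease from both arms, which fits 8.1.2. The causality table in 8.1.4 makes bone disease a reportable cause in its own right, apart from RT. Within the 8.2.3 list, the fluctuations bullet stops at worsening, and the procedures bullet gives way when the underlying condition is an (S)AE. The elective-admission bullet is the only one of these that asks whether the treatment was the cause.

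**Step 3. What falls outside the conflict**

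The bullet covers only admissions that are elective and for a pre-existing condition. Emergency admissions and admissions for lesions that arose after baseline are not exempted by it in either arm. SSEs are reported to the study team directly (Table 1, footnote h) and registered in both arms (footnote j). Hospitalizations related to the high-risk metastases are logged separately in both arms (footnote i). The primary endpoint and the hospitalization endpoint therefore do not depend on SAE status.

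**Step 4. Effect on SAE counts by arm**

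Let a and b be the numbers of elective admissions for worsened baseline metastases in arms A and B, p the share of b attributed to RT, and f the share of all such admissions that sites handle by the 8.2.3 bullet, taken as equal in both arms.

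- SAEs filed in arm A: (1 − f) × a
- SAEs filed in arm B: (1 − f) × b + f × p × b
- Difference, A minus B: (1 − f) × (a − b) − f × p × b

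With f = 0 (all sites use 8.1.2) the difference is a − b. With f = 1 and p = 0 it is 0. With f = 1 and p above 0 it is −p × b. The protocol gives none of a, b, p or f, so neither the size nor the sign of a distortion follows from it.

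**The case against.** The strongest reply is that other text already catches most of these cases. Section 8.2.2 still demands bone-disease (S)AEs from both arms. Planned surgery for an impending fracture can be read under the procedures bullet, which keeps it reportable if the underlying condition is an (S)AE. Pathological fractures, and impending fractures with a Mirels score of 9 or more for which stabilization is recommended, are excluded at entry (section 4.3), so such a fracture is arguably a new diagnosis and not a pre-existing condition. Hospitalization, the relevant seriousness criterion, can be reconstructed from the footnote i log, which holds the dates and any link to an SSE. The bullet governs SAE reporting only, so the underlying event may still be entered as an AE with its CTCAE grade. The protocol names no between-arm comparison of SAEs as such.

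All of this narrows the consequences and is accepted. It does not remove the contradiction. The metastasis itself is pre-existing, so a site may reasonably apply the elective bullet, and the same admission can then be exempt under one bullet and not under another. The hospitalization log also does not trigger the 24-hour notice.

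A reader might go further and infer that these admissions always vanish from the SAE data in arm A, and that the SAE comparison reverses against RT. The documents do not support that. Natural progression is exempt under 8.2.3 in arm B as well. The reading also needs the treatment to mean study RT, while section 3.1 calls both arms treatment arms.

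A reversal further needs an attribution share that the protocol does not give. For scale, the design's 48 patients per arm without drop-out and 2-year event-free rates of 20% and 45% give 48 × 0.80 = 38.4 and 48 × 0.55 = 26.4 first events. The total of 64.8 matches the stated 65. Assume that 40–80% of these are SSEs and that 10–30% of those lead to an elective admission. Arm A then has 38.4 × 0.04 = 1.5 to 38.4 × 0.24 = 9.2 admissions, and arm B 26.4 × 0.04 = 1.1 to 26.4 × 0.24 = 6.3. If every site used 8.2.3, arm A would file 0, and arm B would file 0 at p = 0 or 0.5 to 3.2 at p = 0.5. The reversal thus comes entirely from the assumed p, and section 10.1.4 expects no high-grade side effects.

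**Conclusion.** The point holds as an internal contradiction in SAE reporting. Sections 8.1.2 and 8.2.2 make an elective admission for a naturally progressed baseline metastasis reportable, and one bullet of 8.2.3 says that it need not be. Inconsistent filing between sites and a missed 24-hour notice are risks that follow from this, not outcomes that the protocol fixes.

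The difference between arms is conditional. It arises only if the treatment means study RT, and only through arm B admissions that an unblinded investigator attributes to RT. Its size and direction cannot be derived from the document. The affected set is narrow, and the consequence is confined to SAE reporting and any safety summary built on it. The correction is nevertheless worth making, because it is nearly free and removes a threshold based on cause from an open-label trial.

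**What to change.** Replace the elective-admission bullet in section 8.2.3 with the protocol's own 8.1.2 test, for example: *Elective hospitalization for a pre-existing condition that has not worsened from baseline*. State that it applies identically in both arms, and carry the same wording into the SAE instructions for sites. Leave the separate 8.2.3 exemption for admissions planned before consent in place. A blanket rule that no admission for a progressed metastasis is ever exempt would override it and is not needed.

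The cost is one sentence in the protocol and the site instructions, plus a few more SAE forms. No data item, endpoint or clinical procedure changes.
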